2.1. Plasma PK endpoints

Blood samples will be drawn:

- For cohorts A, B and C:
 - on Day 1 at pre-dose then post-dose (after start of infusion) at H0.5, H1, H1.5, H2, H4, H6, H6.5, H7, H7.5, H8, H10, H12, H16, then at D2 (H24), D3 (H48), D4 (H72) and D5 (H96).
In case of infusion less than 6 hours, blood sample for Ir-CPI pharmacokinetics will be done at the end of infusion then H0.5, H1, H1.5, H2, H4, H6, H10, H18, H42, H66 and H90 after the end of infusion.
- For cohort D:
 - on Day 1 at pre-dose then post-dose (after start of infusion) at H0.5, H1, H1.5, H2, H4, H6, H6.5, H7, H7.5, H8, H10, H12, H16, then at D2 (H24), D3 (H48), D4 (H72), D5 (H96) and D7 (H144).
In case of infusion less than 6 hours, blood sample for Ir-CPI pharmacokinetics will be done at the end of infusion then H0.5, H1, H1.5, H2, H4, H6, H10, H18, H42, H66, H90 and H138 after the end of infusion.

2.2. Plasma pharmacokinetic analysis

The compartmental pharmacokinetic analysis will be performed on the Pharmacokinetic set (PKS) defined in the final SAP as all of the included participants who have been administered a complete infusion of IMP without major protocol deviation affecting PK evaluation.

Subjects receiving placebo will not be included in the summary and analysis of PK parameters.

Graphical exploration of plasma concentrations versus time profiles will be performed by subject and by group.

For the description of individual plasma concentration-time profiles, one-, two- and three compartment models will be investigated using non-linear regression from models of the Phoenix WinNonlin library.

To assess how the compartmental model explains the individual concentration data:

- The evaluation of the goodness of fit and the estimated parameters will be based, but not only, on the Akaike information criterion, the Schwarz Bayesian Criterion (SBC), the coefficient of variability (CV) of the parameter estimates, the random distribution of residuals (weighted or not) between measured and predicted concentrations with respect to time, correlation between independent model parameters (<0.95) will be checked to select the model that best fits the observed data.
- Individual plots of observed and predicted concentrations, residual versus (vs.) predicted concentrations and residual vs. time profiles of Ir-CPI will be presented graphically on linear and log/linear coordinates with the PK model selected to best fits the observed data.
- Relevant plasma PK parameters will be calculated for Ir-CPI by compartmental methods, as appropriate for those participants with sufficient plasma concentration data. PK parameters obtained by compartmental analysis including descriptive statistics will be presented in tables separately for each treatment group.

3. Pharmacokinetic-Pharmacodynamic analysis

The evaluation of the relationship between plasma concentrations of Ir-CPI and the PD parameters, i.e. the change from baseline in coagulation parameters (i.e. aPTT ratio), FXI and FXII inhibition are graphically investigated and displayed according to the final SAP.

3.1. Plasma PD endpoints

Effect of Ir-CPI on PD aPTT, Factor XI and Factor XII inhibition will be measured by the change from baseline (central lab). PD aPTT and FXI/FXII parameters will be measured:

- For cohorts A, B and C:
 - on D1, pre-dose then at 30min, 60min, 90min, 2h, 4h, 6h, 6h30, 7h, 7h30, 8h, 10h, 12h, 16h post-dose, then on D2 (24h), D3 (48h), D4 (72h), D5 (96h) and discharge visit (D10 ± 2 days).
In case of infusion less than 6 hours and besides assessment at pre-dose, 30 min, 60 min, 90 min, 2h and 4h after start of infusion, parameters should be measured at the end of infusion, then 30min, 60 min, 90min, 2h, 4h, 6h, 10h, then 18h, 42h, 66h and 90h after the end of infusion and then at the discharge visit.
- For cohort D:
 - on D1, pre-dose then at 30min, 60min, 90min, 2h, 4h, 6h, 6h30, 7h, 7h30, 8h, 10h, 12h, 16h post-dose, then on D2 (24h), D3 (48h), D4 (72h), D5 (96h), D7 (144h) and discharge visit (D10 ± 2 days).
In case of infusion less than 6 hours and besides assessment at pre-dose, 30 min, 60 min, 90 min, 2h and 4h after start of infusion, parameters should be measured at the end of infusion, then 30min, 60min, 90min, 2h, 4h, 6h, 10h, then 18h, 42h, 66h, 90h and 138h after the end of infusion and then at the discharge visit.

For each time point, including the baseline time point, an aPTT ratio was calculated by dividing the aPTT value (in sec) of the specific time point (aPTT*) by the baseline aPTT value (in sec) (aPTT°) of the same volunteer (aPTT ratio = aPTT*/aPTT°). This ratio in function of the time will be used. The baseline time-point is considered as having an aPTT ratio of 1.

Concerning FXI and FXII PD parameters, individual data of FXI activity and FXII activity in function of the time will be used. Moreover, FXI or FXII inhibition, expressed in percentages, for each time point (including the baseline time point), were calculated for each volunteer according to the main SAP:

- Percentage of FXI inhibition= $100 - [(FXI^*/FXI^\circ) * 100]$
- Percentage of FXII inhibition= $100 - [(FXII^*/FXII^\circ) * 100]$

In case of negative values, these values will be replaced by 0 (for the main and post-hoc analyses).

FXI or FXII*:* FXI or FXII percentage of inhibition of a specific time point

FXI° or FXII°: FXI or FXII percentage of inhibition of the baseline time point

The baseline time point is considered as 0 % of FXI or FXII inhibition.

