4. OBJECTIVES AND ENDPOINTS

Objectives	Endpoints
Primary	
Part 1: Assess the safety and tolerability of Ir-CPI following a single ascending 6-hour intravenous infusion in healthy male participants.	Safety parameters [adverse events (AEs), physical examinations, vital signs, telemetry including SpO ₂ , weight, Hemocult® test, supine 12-lead ECG, serum chemistry, haematology, coagulation aPTT, urinalysis, and monitoring for concomitant medications].
Part 2*: Assess the safety and tolerability of Ir-CPI following a combination of rapid (30 minutes) and slow (5.5 hours) intravenous infusion over a total of 6 hours in healthy male participants.	
Secondary	
Part 1: Assess the PK of Ir-CPI following single ascending 6-hour intravenous infusion in healthy male participants.	Maximum plasma concentration (C _{max}), time to reach maximum plasma concentration (t _{max}), Area under the plasma concentration-time curve from time zero to 6h (AUC ₀₋₆), Area under the plasma concentration-time curve from time zero to time of infinity (AUC _{inf}), apparent terminal elimination rate constant (λ _z), terminal elimination half-life (t _{1/2}), volume of distribution (Vd), total body clearance (CL).
Part 2*: Assess the pharmacokinetics (PK) of Ir-CPI following a combination of rapid (30 minutes) and slow (5.5 hours) intravenous infusion over a total of 6 hours in healthy male participants.	
Investigate the preliminary PD of Ir-CPI in healthy male participants using a GCLP validated method according to FDA guidelines 2018 for activated Partial Thromboplastin Time (aPTT). Inhibition of Factor XI (FXI) and Factor XII (FXII) procoagulant activities will also be assessed to support the aPTT dynamics.	Change from baseline in aPTT and residual FXI and FXII activities.
Exploratory	
Investigate the potential of Ir-CPI to induce the formation of anti-drug antibodies (ADA), including their capability to neutralize drug activity.	Immunogenicity assessed by ADA plasma levels.
Investigate the effect of Ir-CPI on markers related to the coagulation system.	D-dimers, fibrinogen and prothrombin time (PT) levels in whole blood.
Investigate the effect of Ir-CPI on biomarkers for renal injury.	Blood assay: serum cystatin C (CysC). Urinary assay: urinary microalbumin, Kidney Injury Molecule (KIM-1), urinary neutrophil gelatinase-associated lipocalin (NGAL).

Objectives	Endpoints

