9.4. Pharmacodynamic Evaluation

9.4.1. Pharmacodynamic outcome measurements

- ***PD aPTT – Factor XI and Factor XII inhibition:*** measured by the change from baseline in PD aPTT and residual FXI and FXII activities (central lab).

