10.2.7.2. Statistical methodology

Analysis of pharmacodynamic parameters will be performed on the Pharmacodynamic set. For each parameter, descriptive statistics will be provided by treatment group on values and changes from baseline for each timepoint.

All pharmacodynamic parameters will be listed.

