6.2. Descriptive statistics and data listings

Descriptive statistics will be supplied according to the nature of the criteria:

- Quantitative variable: sample size, arithmetic mean, standard deviation (SD), standard error of the mean (SEM), minimum, median and maximum, and [quartiles if necessary with geometric mean, arithmetic and geometric coefficients of variation (CV), and quartiles for PK parameters].
- Qualitative variable: sample size, absolute and relative frequencies per class. Percentages will be provided with one decimal place.

If the sample size of one treatment group is less than or equal to 2, only the number of observed values, the minimum and the maximum will be presented for quantitative variables and the percentage of subjects will not be presented for qualitative variables.

Unless specified otherwise, the calculation of percentages will be based on the number of observed values. Therefore, counts of missing values will be included in the denominator and displayed as a separate category if any.

Data will be organised by treatment group:

- Pooled Placebo;
- Ir-CPI 1.5 mg/kg;
- Ir-CPI 3 mg/kg;
- Ir-CPI 6 mg/kg;
- Ir-CPI 9 mg/kg.

All demographic, pharmacokinetics, pharmacodynamics, safety and tolerability listings will be sorted by treatment group, subject and measurement time if applicable.

All listings containing an evaluation date will display the study day defined as the day relative to the administration of study drug:

- Study day 1 will be defined as the day of the study product administration date;
- Study day -1 will be defined as the day prior to the study product administration date;
- There will be no study day 0.

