Concerning FXI and FXII PD parameters, a graphical representation of individual data of FXI activity in each cohort, in function of the time, will be done. Another graphical representation of FXII activity in each cohort, in function of the time, will be done. In these graphs, the normal lower ranges of FXI and FXII activities will be indicated as horizontal lines.

Moreover, FXI or FXII inhibition, expressed in percentages, for each time point (including the baseline time point), has to be calculated for each volunteer. To do so, the calculation is the following:

- Percentage of FXI inhibition= $(100 - ((FXI^*/FXI^\circ) * 100))$
- Percentage of FXII inhibition= $(100 - ((FXII^*/FXII^\circ) * 100))$

FXI* or FXII*: FXI or FXII percentage of inhibition of a specific time point

FXI° or FXII°: FXI or FXII percentage of inhibition of the baseline time point

The baseline time point is considered as 0 % of FXI or FXII inhibition. A graphical representation of FXI or FXII inhibition, expressed as percentages, in function of the time will be done per volunteer. The mean \pm SEM, min and max curves will be also represented for each cohort on separate graphs. The mean \pm SEM curves of all cohorts (A, B, C, D) will be also represented on a same graph.

Descriptive statistics of changes from baseline will be provided by treatment group and each measurement time for changes from baseline of aPTT ratio and absolute values.

Descriptive statistics will be provided by treatment group on each measurement time for aPTT values (absolute values and changes from baseline), aPTT ratio (ratio values and changes from baseline of ratios) and percentage of FXI or FXII inhibition (calculated percentages and changes from baseline of percentages).

All pharmacodynamics parameters will be listed.

11. Exploratory Pharmacokinetic / Pharmacodynamic analysis

Evaluation of the relationship between concentrations of Ir-CPI and the PD parameters: the change from baseline in coagulation parameters (i.e. aPTT ratio) defined above, FXI and FXII inhibition will be graphically investigated and displayed. The analysis will be performed on the PDS.

12. Exploratory Biomarkers Evaluation

The exploratory biomarkers evaluation will be performed on the PDS.

The following exploratory outcome measurements are defined:

- In blood: D-dimers, fibrinogen, prothrombin time PT (expressed in seconds and as INR), TNF α , hsCRP, cystatin C (CysC), ADA.

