Protocol Number: Clin_IrCPI_101**Version and date: 4.0 – 06DEC2019**

TITLE: Appendix to the final Statistical Analysis Plan for compartmental pharmacokinetic analysis of Ir-CPI plasma concentrations, Pharmacokinetic-Pharmacodynamic analysis and Anti-Drug Antibodies analysis

Date: 13AUG2020 - Version: Final version 1.0

1. Introduction

This appendix covers the details of the post-hoc analyses on Pharmacokinetics (PK), pharmacokinetics/pharmacodynamics (PK/PD) and Anti-Drug Antibodies (ADA) data from Clin_IrCPI_101 study as well as anticipated data transformations and manipulations. It completes the final Statistical Analysis Plan (SAP) (version V1.0 dated 09 July 2020) and it is based on Sponsor requests.

This SAP will support additional post-hoc analyses on:

- PK data and PK/PD endpoints performed by the Pharmacokineticist of BIOTRIAL in agreement with the Sponsor.
- ADA data (presence, titration, sub-classes and the capability to neutralize drug activity) performed by the Biostatistics unit of BIOTRIAL BIOMETRICS in agreement with the Sponsor.

PK and PK/PD parameters will be calculated using Phoenix[®] WinNonlin[®] version 8.1 Certara USA, Inc., Princeton, NJ) and ADA analysis will be performed using SAS[®] software version 9.4 (SAS institute Inc. Cary NC USA).

In accordance with the Sponsor, negative values, identified after the calculation of Factor XI and Factor XII inhibition in the main analysis, will be replaced by 0.

2. Compartmental pharmacokinetic analysis

The rules defined in the section **Erreur ! Source du renvoi introuvable.** of the final SAP will be used.

The actual blood sampling time and infusion duration will be used. The theoretical dose (mg/kg) will be used.

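### Setting negative FXI/FXII percent inhibition to 0, after the negatives had been seen, raises group means and shrinks SEMs wherever true inhibition is near 0

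*SAP*

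**What the plan says.** The protocol (section 4) gives the secondary pharmacodynamic endpoint as "Change from baseline in aPTT and residual FXI and FXII activities". Section 9.4.1 says that FXI and FXII inhibition is "measured by the change from baseline in PD aPTT and residual FXI and FXII activities (central lab"). Section 10.2.7.2 plans that "descriptive statistics will be provided by treatment group on values and changes from baseline for each timepoint".

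SAP section 10 (Pharmacodynamics data) defines percent inhibition as 100 − 100 × (FXI\*/FXI°), with the same form for FXII and no lower bound. Baseline inhibition is taken as 0%. For these factors it names group statistics only for "percentage of FXI or FXII inhibition (calculated percentages and changes from baseline of percentages"). SAP section 6.2 lists those statistics as sample size, "arithmetic mean, standard deviation (SD), standard error of the mean (SEM), minimum, median and maximum", organised by treatment group including pooled placebo. Mean ± SEM and minimum/maximum curves are also planned (outputs 14.2.2.4 and 14.2.2.5).

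The SAP appendix of 13 August 2020 postdates SAP V1.0 (9 July 2020). Its introduction says, by agreement with the sponsor, that "negative values, identified after the calculation of Factor XI and Factor XII inhibition in the main analysis, will be replaced by 0". Its section 3.1 gives the scope: "In case of negative values, these values will be replaced by 0 (for the main and post-hoc analyses"). It gives no scientific reason, no count of values replaced and no analysis with the values left as calculated.

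**The concern.** A negative inhibition value means only that post-dose activity was above baseline. Without a drug effect, about half of all values should be negative through assay and biological scatter. Setting those to 0 while keeping the positive half removes one side of the noise. What remains looks like a small, precisely measured inhibition.

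This matters most where the truth is close to 0: pooled placebo, and times when concentrations are low. There the tables and group graphs would tend to show some inhibition, with an error bar clear of 0 and a minimum curve lying on 0. Because the group nearest 0 is raised most, the gap between active and placebo is understated. The low end of the concentration–inhibition graphs, and any FXI/FXII model fit, is affected in the same way; placebo participants are included in the PK-PD analysis (appendix section 3.2). The rule also changes a main-analysis derivation after the values it alters had been seen.

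**Working it through.** The plan gives no figure to reproduce here and no SD for FXI or FXII inhibition. The direction follows from algebra. Sizes are therefore in SD units first, then in percentage points under stated assumptions.

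**Inputs.** Each panel has 6 active and 2 placebo participants (SAP section 4), and there are four panels (SAP section 3.2), so pooled placebo is 4 × 2 = 8. Baseline inhibition is 0 by definition, so the change from baseline equals the percentage itself and is floored too.

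**Direction.** Let y = max(x, 0).
- The group mean rises by (sum of |negative x|)/n.
- No pairwise difference |yᵢ − yⱼ| exceeds |xᵢ − xⱼ|, so the SD and SEM cannot rise.
- A check on 100,000 simulated groups of 8 found no violation.

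**Size with normal scatter.** With true mean μ and SD s, E[max(0, X)] = μΦ(μ/s) + sφ(μ/s), and the floored SD comes from the second moment.

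| μ/s | values below 0 | rise in mean | floored SD / true SD |
|---|---|---|---|
| 0 | 50% | 0.40 s | 0.58 |
| 0.5 | 31% | 0.20 s | 0.74 |
| 1 | 16% | 0.08 s | 0.87 |
| 2 | 2% | 0.01 s | 0.98 |

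The median moves less. For n = 8, by simulation, it rises by 0.18 s at μ = 0 and by 0.03 s at μ = 0.5 s.

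**How often placebo looks inhibited (n = 8, true inhibition 0).** For non-negative values, mean > SEM is the same as (Σx)² > Σx², which holds exactly when at least two values are positive. With independent values and median 0:

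- Floored: 1 − (1 + 8)/2⁸ = 1 − 9/256 = 96.5%.
- Unfloored, normal scatter: P(t with 7 df > 1) = 17.5%.
- Unfloored, lognormal error of 5%, 10% or 15% CV in both baseline and post-dose values: 16%, 15% or 13%.
- Floored minimum exactly 0: 1 − 0.5⁸ = 99.6%.

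**In percentage points (SD assumed).**

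| assumed SD | true 0 reported as | SEM, n = 8 | true difference of 10 (active 10, placebo 0) reported as |
|---|---|---|---|
| 5 | +2.0 | 1.77 → 1.03 | 10.04 − 1.99 = 8.0 |
| 10 | +4.0 | 3.54 → 2.06 | 10.83 − 3.99 = 6.8 |
| 15 | +6.0 | 5.30 → 3.10 | 12.27 − 5.98 = 6.3 |

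At 15% true inhibition, the in vitro FXII figure in protocol section 5.6, the bias is 0.0, 0.3 or 1.2 points for these three SDs.

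**Check with the ratio itself.** The formula 100 − 100 × (post/baseline) was simulated with lognormal activities, n = 8 and true inhibition 0. At assumed CVs of 5%, 8% and 10% per measurement, the mean went from −0.24, −0.64 and −1.00 to +2.70, +4.21 and +5.16. The average SEM went from 2.42, 3.88 and 4.87 to 1.28, 1.98 and 2.42.

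**Legend.** SAP section 10 describes FXI° and FXII° as "FXI or FXII percentage of inhibition of the baseline time point", and appendix section 3.1 repeats this. Baseline inhibition is set to 0, so read literally the formula divides by 0. It works only if the symbols mean residual activity.

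**The case against.** The strongest case against is that little depends on this. FXI/FXII activity is secondary and supports aPTT; the aPTT ratio is not floored. No test, dose decision or stopping rule uses inhibition. The rule is disclosed, dated and applied alike to every group. It understates active–placebo separation, so it does not manufacture a drug effect. Individual activity is plotted without a floor (output 14.2.2.6) and listed, and appendix section 3.1 also draws on activity data. FXI/FXII modelling is optional. All of this stands, and it limits the seriousness of the point. It does not repair the group tables and graphs, because a reader cannot undo the bias in a mean from individual plots.

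Three narrower objections:

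- **Protocol criteria.** Section 10.2.7.1 lists FXI and FXII inhibition, not residual activity, so summarising inhibition is consistent with it. That is fair as far as it goes. But section 9.4.1 defines inhibition through the change in residual activity, so a group summary of activity is what the two sections together support.
- **Placebo on the graphs.** SAP section 10 describes the combined graph as showing cohorts A to D, so pooled placebo may not appear on output 14.2.2.5. This stands as an uncertainty. Placebo does belong in the tables and, by its title, in output 14.2.2.4.
- **Group size.** The 96.5% needs all 8 placebo participants in the pharmacodynamic set and a median of 0. With 6 it is 1 − 7/64 = 89%. The conclusion does not change.

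**Conclusion.** The concern holds and should be fixed. The rule adds a one-sided bias to the only FXI/FXII group statistics the SAP names, and it was introduced after the affected values were known. The direction needs no assumption. The 0.40 SD rise and the 0.58 SD ratio assume normal scatter around a true 0. The 96.5% assumes eight independent values with median 0. The percentage-point figures rest on assumed SDs of 5 to 15 points. At 2 SD of true inhibition the rise in the mean is about 0.01 SD, so strongly inhibited timepoints are essentially unaffected. The legend error is clerical and does not carry the point.

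**What to change.** 1. Delete the replacement rule from the introduction and section 3.1 of the 13 August 2020 appendix.
2. Use untruncated inhibition in the tables, the mean ± SEM and minimum/maximum graphs, the concentration–inhibition graphs and any FXI/FXII fit.
3. If a floored version is kept, show it only as an additional display labelled post hoc, with the number of values replaced per group and timepoint.
4. State in SAP section 10 that residual FXI and FXII activity and its change from baseline are summarised by treatment group, in line with protocol sections 4, 9.4.1 and 10.2.7.2.
5. Correct the legends in SAP section 10 and appendix section 3.1, so that the starred and degree symbols mean residual activity (%) at the timepoint and at baseline.

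The cost is wording changes and a rerun of the FXI/FXII inhibition tables and graphs. No new data are needed. Some plotted values will fall below 0, which a footnote can explain as post-dose activity above baseline.

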3.2. PK-PD analysis

The pharmacokinetic-pharmacodynamic analysis will be performed on the Pharmacodynamic set (PDS) defined in the final SAP as all the included participants who have completed the study without any protocol deviation affecting PD evaluation and with at least one available post-baseline data.

Subjects receiving placebo will be included in the summary and analysis of PK-PD relationship.

The rationale for PK/PD analysis is to link pharmacokinetics and pharmacodynamics in order to establish and evaluate dose-concentration-response relationships and subsequently describe and predict the effect-time courses resulting from a drug dose. PK-PD relationship will be investigated mainly to assess potential correlation between Ir-CPI exposure and the aPTT ratio.

The pharmacokinetic-pharmacodynamic analysis dedicated to FXI and FXII responses will be investigated (or not if considered not appropriate) based on exploratory analysis of the main SAP.

The preliminary graphical exploration will be performed in order to assess the effect of Ir-CPI on aPTT ratio with the dose, the pattern of the relationship for the previous PD model, the linearity assumption and the potential hysteresis between concentrations and response.

The model development will be based on the evaluation of the relation between effect and concentration using non-linear regression from model of the Phoenix WinNonlin library. A direct effect relationship was assumed for aPTT according to the safety aPTT data from interim analysis.

To compare structural models, the evaluation of the goodness of fit and the estimated parameters will be based, but not only, on the Akaike information criterion, the coefficient of variability (CV) of the parameter estimates, the random distribution of residuals between measured and predicted concentrations with respect to time, correlation between independent model parameters (<0.95) will be checked.

Plots of concentration-effect relationship between concentrations versus the corresponding aPTT ratio after Ir-CPI administration will be presented graphically with the PK-PD model selected to best fits the observed data (observed and fitted data).

Relevant PK-PD parameters estimated from the selected model will be described.

4. ADA analysis

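### The appendix's PK-PD regression has no participant-level term and reads most naturally as a pooled fit; if it is pooled, the CVs of its EC50 and Emax are too small, by an amount the documents do not fix

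*SAP*

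**What the plan says.** Section 3.2 of the SAP appendix of 13AUG2020 covers the PK-PD analysis, on the Pharmacodynamic set. The model is to be "based on the evaluation of the relation between effect and concentration using non-linear regression from model of the Phoenix WinNonlin library", with a direct effect assumed for aPTT. On placebo it says: "Subjects receiving placebo will be included in the summary and analysis of PK-PD relationship". Structural models are compared on an open-ended list: "the Akaike information criterion, the coefficient of variability (CV) of the parameter estimates, the random distribution of residuals between measured and predicted concentrations", plus correlation between parameters. For output it says: "Relevant PK-PD parameters estimated from the selected model will be described".

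Section 2.2 of the same appendix, on compartmental PK, uses the same type of regression from the same software library but states the unit of fitting: "For the description of individual plasma concentration-time profiles, one-, two- and three compartment models will be investigated using non-linear regression". It excludes placebo and reports parameters with descriptive statistics by treatment group.

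Section 3.1 divides each aPTT value by the same participant's baseline value and sets the baseline ratio to 1. Neither section 3.1 nor section 3.2 mentions a random effect, a cluster adjustment, a weighting scheme or a concentration value for placebo samples.

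**The concern.** Section 3.2 departs from section 2.2 in three ways: it does not say that fits are individual, it brings placebo in, and it speaks of parameters from one selected model. A placebo participant contributes no spread of concentrations, so no individual concentration-effect curve can be estimated for him. He can contribute only to a fit across participants.

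In a pooled non-linear regression, the standard errors, and hence the parameter CVs, are computed as if every sample were a separate piece of evidence. Here the samples come in blocks of about 18 per person and are linked in two ways. Each participant has his own sensitivity to the drug, and every ratio he contributes carries the measurement error of a single pre-dose aPTT. AIC rests on the same independence assumption.

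The appendix says the model should help predict the time course of effect after a dose, and the protocol synopsis says the study's results will feed proof-of-concept studies. An EC50 reported with too small a CV would make the concentration-aPTT relation look better known than 32 participants allow.

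**Working it through.** **1. Count of pairs.** The PK schedule (appendix section 2.1) is "on Day 1 at pre-dose then post-dose (after start of infusion) at H0.5, H1, H1.5, H2, H4, H6, H6.5, H7, H7.5, H8", then H10, H12, H16, H24, H48, H72 and H96. That is 11 + 7 = 18 samples in cohorts A to C, and 19 in cohort D, which adds H144. The PD schedule (section 3.1) has the same times plus the discharge visit, which has no PK sample. SAP sections 3.2 and 4 give four cohorts of 6 active and 2 placebo.

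- All participants: 24 × 18 + 8 × 19 = 432 + 152 = 584 pairs, or 584/32 = 18.25 per person.
- Active only: 18 × 18 + 6 × 19 = 324 + 114 = 438 pairs.
- Placebo: 584 − 438 = 146 pairs.
- Baseline ratios are 1 by definition, so 584 − 32 = 552 pairs can vary.

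**2. Order of magnitude.** The documents give no CV, standard error or intra-participant correlation (ICC) for this model, so there is no plan figure to reproduce. The usual clustering factor, √(1 + (m − 1) × ICC) with m = 18, gives:

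| ICC | 0 | 0.1 | 0.3 | 0.5 | 1 |
|---|---|---|---|---|---|
| Factor | 1.00 | 1.64 | 2.47 | 3.08 | 4.24 |

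This is orientation only. The formula is for a mean, or for a covariate constant within a person, whereas concentration varies within a person.

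**3. Simulation of a pooled, unweighted Emax fit.** The design was 24 active and 8 placebo participants, doses of 1.5, 3, 6 and 9 mg/kg, the planned times and baseline ratio set to 1. Assumed: CL 80 mL/h/kg (protocol section 5.6), two-exponential concentration curves, Emax 2.5, EC50 5 µg/mL, the same between-participant log SD on both, and additive residual error on the ratio. The shared pre-dose error was 5 % wherever the between-participant SD exceeded 0. There were 500 trials per setting. The factor is the spread of the estimates divided by the median pooled-fit standard error, with EC50 and Emax on the log scale.

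| Between-participant SD | EC50 factor at residual SD 0.05 / 0.15 / 0.30 | Emax factor at the same |
|---|---|---|
| 0 | 1.06 / 1.01 / 1.09 | 1.07 / 1.04 / 1.11 |
| 0.05 | 2.69 / 1.91 / 1.28 | 3.50 / 2.30 / 1.47 |
| 0.10 | 3.20 / 2.10 / 1.53 | 3.86 / 2.89 / 1.75 |
| 0.20 | 3.46 / 2.52 / 2.08 | 4.54 / 3.48 / 2.60 |
| 0.30 | 3.16 / 3.00 / 2.39 | 4.33 / 4.24 / 3.11 |

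With a linear model instead, the slope factor ran from 1.5 to 7.6 where participants varied. The baseline term of the Emax model ran from 0.80 to 1.72, so not every parameter's CV is understated.

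**4. A second set of assumptions, tied to protocol figures.** One-compartment PK: (1.5/0.08)(1 − e^(−6k)) = 8.3 gives k = 0.0974/h. Emax 3 and EC50 5.5 µg/mL give 1 + 3 × 0.5/(5.5 + 0.5) = 1.25, matching the protocol's 25 % aPTT increase at 0.5 µg/mL. Assumed: PK log SD 0.2 and proportional assay error of 5 to 8 %. EC50 factors:

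| EC50 log SD | Pre-dose denominator noisy | Denominator without noise |
|---|---|---|
| 0.2 to 0.4 | 2.5 to 3.7 across repeat runs | 2.1 to 2.9 |
| 0.1 | not run | 1.6 to 1.8 |
| 0 | 2.3 to 2.5 | about 1.35 |

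The last row separates the mechanisms. With no sensitivity differences, the shared denominator alone still gives a factor above 2. The residual 1.35 is consistent with an unweighted fit to proportional error rather than with clustering.

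**The case against.** The strongest reply is that the appendix never says the data are pooled. Section 2.2 uses the same wording about the same library for individual profiles. Placebo inclusion covers summary as well as analysis, and so could refer to plots and tables only. The fitted model is to be displayed for aPTT ratios after Ir-CPI, which suggests active participants. SAP section 9.1 leaves wholly unquantifiable profiles unreplaced and out of the PK analysis, and no rule gives placebo a numeric concentration for PK-PD. If each active participant is fitted separately, the between-participant mechanism disappears. All of this stands as a reason not to call pooling a fact. It does not clear the text: on the individual reading, the placebo sentence cannot apply to the fit, so section 3.2 needs correcting either way.

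The second reply concerns consequence, and it also stands. The analysis is post-hoc at the sponsor's request, and the protocol promised only graphical PK-PD work. No test or decision rule uses the estimates. CV and AIC are two criteria among several.

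Two further inferences are tempting but unsupported. A reader might quote poor confidence-interval coverage, but the appendix plans no interval for EC50 or for predicted aPTT. A reader might also infer that over-complex models will be chosen. AIC does assume independence, but the effect on model choice was not tested.

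**Conclusion.** The point holds conditionally. Section 3.2 leaves open the unit of fitting, the role of placebo in the fit and the handling of repeated samples. A pooled fit is the natural reading because placebo participants cannot be fitted individually. If the fit is pooled without a participant-level term, the CVs of EC50 and Emax are too small.

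A reader might infer a fixed factor, such as 2.5 to 3.5. The documents do not support one: they give no between-participant variance for the response, no assay CV, no Emax and no weighting. Under the assumed settings the EC50 factor is roughly 1.4 to 3.5. Single settings fall slightly outside (1.3 and 3.7), and it is about 1 with additive error, no participant differences and no shared baseline error. The upper part of the range needs clear sensitivity differences, a noisy pre-dose denominator, or both. An Emax form is itself an assumption, since the appendix commits only to a direct-effect library model.

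This is worth correcting because a better method is available at small cost. It does not threaten the trial's primary safety conclusions.

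**What to change.** State the unit of fitting in section 3.2, then take one of three routes.

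- **Preferred:** a non-linear mixed-effects model with a participant random effect on EC50 (or on slope, if the model is linear) and a term for the baseline error shared by all of a participant's ratios. SAS 9.4 is already named in the SAP. This route was not simulated here.
- **Alternative:** keep the pooled fit, but take all parameter CVs from a bootstrap that resamples whole participants within dose group. In simulation its standard errors were 2.4 to 2.5 times the pooled ones. Nominal 95 % intervals built from it still covered only 82 to 89 %, so the report should say that with 32 participants it may remain somewhat too narrow.
- **If individual fits were intended:** say so, restrict the fit to active participants, summarise the individual parameters, and keep placebo for graphs and descriptive tables.

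If placebo stays in a pooled or mixed-effects fit, state what concentration its samples carry. State the residual weighting on any route.

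The cost is some extra programming on an exploratory, post-hoc analysis, and reported precision that looks less favourable.
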